12.4. Definitions of Secondary Endpoints

- Toxicity and tolerability: The occurrence and rate of any AEs, SAEs, AESIs, or imAEs while being on study drug and up to 30 days of receiving the final dose of the study drug.

12.5. Definitions of Correlative Endpoints

- Programmed death ligand -1 expression at cellular level in the specimen of residual tissue obtained at the time of esophagectomy
- Assessment of tumor infiltrating lymphocytes by histologic analysis within the tumor and in surrounding connective tissue
- Immunoscore (based on numeration of lymphocyte populations CD3/CD45RO, CD3/CD8, CD8/CD45RO) within the tumor and in surrounding connective tissue
- Changes in the circulating tumor cells collected at baseline, at 3 months, and at the time of disease recurrence (during treatment or follow up).

12.6. Sample Size/Accrual/Study Duration/Replacement Rules

Historical outcomes of patients who receive chemoradiotherapy followed by surgical resection and are noted to have persistent disease at the time of surgery are poor with 50% of them recurring in the first year (34). We expect durvalumab to improve the relapse free survival at 1 year rate by 25%. The null hypothesis is that 1 year RFS with postoperative adjuvant durvalumab therapy in patients with persistent esophageal cancer following neoadjuvant chemoradiotherapy and esophagectomy is 50% or less. Alternative hypothesis is that 1 year RFS with postoperative adjuvant durvalumab therapy in patients with persistent esophageal cancer following neoadjuvant chemoradiotherapy and esophagectomy is 75% or greater. With a maximum acceptable type I error (the probability of concluding that the drug is effective when it is actually not effective) of 0.05, and acceptable type II error (the probability of concluding that the drug is not effective when it is actually effective) of 0.20, the calculated sample size is 23 evaluable patients. If the total number of patients free of relapse at 1 year is less than or equal to 15, the drug would not be considered for further study. Up to 26 will be enrolled to allow for 10% unevaluable for efficacy. Subjects who receive less than 6 months of durvalumab for reasons unrelated to disease progression or toxicity will be replaced. Estimated accrual period is 18 months; follow up period of 12 months. To improve accuracy for estimating the primary endpoint (1 year RFS) with a 95% confidence interval, an additional 11-16 patients beyond the initial planned 23 evaluable will be enrolled for a target of 39 enrolled and at least 34 patients evaluable for 1 year RFS (to allow for approximately 10% unevaluable). With n=34 evaluable, if the 1 year RFS is 75%, a 95% two-sided confidence interval will have a half-width of 15% (using normal-approximation).

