OBJECTIVES	 Primary Objective: To determine if postoperative adjuvant therapy with durvalumab improves 1 year relapse free survival (RFS) compared to historical rates in patients with persistent esophageal cancer following neoadjuvant chemoradiotherapy and esophagectomy 			
	 Secondary Objectives: To assess the toxicity and tolerability of durvalumab following trimodality therapy in patients with esophageal cancer. 			
	 Correlative Objectives: To assess changes in PD-L1 expression with chemoradiotherapy in esophageal cancer. To analyze possible predictive biomarkers of 1 year RFS including PD-L1 expression (at diagnosis and in residual disease) in tumor cells and tumor infiltrating lymphocytes (by histology and gene expression analysis – by pathway analysis and CIBERSORT), both within the tumor and in surrounding connective tissue. To assess the Immunoscore (based on numeration of lymphocyte populations - CD3/CD45RO, CD3/CD8, CD8/CD45RO) – within the center and invasive margins of the tumor – and correlate with 1 year RFS. To analyze the correlation between changes in circulating tumor cell numbers in response to PD-L1 inhibition and 1 year RFS in patients 			
OUTCOME MEASURES	 Primary: Relapse free survival (RFS) at 1 year Secondary: Incidence and severity of adverse events overall and related to the study drug. Exploratory outcomes as above. 			
STUDY DESIGN	Phase II, open-label, single arm, single-stage study. A total of 23 evaluable patients will be enrolled (26 total to account for 10% unevaluable). If total number of patients free of disease relapse at 1 year is less than or equal to 15, the drug would not be considered for further study in this setting. To improve accuracy for estimating the primary endpoint (1 year RFS) with a 95% confidence interval, an additional 11-16 patients beyond the initial planned 23 evaluable will be enrolled for a target of 34-39 enrolled to have at least 34 patients evaluable for 1 year RFS.			

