	 Patients with diagnosis of immunodeficiency or those receiving chronic systemic corticosteroid therapy or other immunosuppressive therapy (except inhaled steroids) within 28 days of the first dose of study drug History of psychiatric illness/social situations that would limit compliance with study requirements. Clinically significant infections as judged by the treating investigator. Clinically significant is defined as an active infection requiring IV antibiotics 				
	- Known HIV infection or chronic hepatitis B or C.				
STATISTICAL	Null Hypothesis: 1 year RFS with postoperative adjuvant durvalumab				
CONSIDERATIONS	therapy in patients with persistent esophageal cancer following neoadjuvant				
	chemoradiotherapy and esophagectomy is 50% or less.				
	Alternative Hypothesis : 1 year RFS with postoperative adjuvant				
	durvalumab therapy in patients with persistent esophageal cancer following				
	neoadjuvant chemoradiotherapy and esophagectomy is 75% or greater.				
	Acceptable Type I (alpha) error: 5%				
	Acceptable Type II (beta) error: 20%				
	Power : 80%				
	Phase II, open label, single arm, single-stage study.				
TOTAL	Total n=39, 34 efficacy evaluable and allowing for up to 5 unevaluable.				
NUMBER OF	Subjects who receive less than 6 months of durvalumab for reasons				
SUBJECTS	unrelated to disease progression or toxicity will be replaced.				
ESTIMATED					
ENROLLMENT	Estimated 18 months				
PERIOD					
ESTIMATED					
STUDY	Estimated 20 months				
DURATION					

INDEX

SECTION PAGE

IE	MA	8
	BACKGROUND & RATIONALE	9
	OBJECTIVES, ENDPOINTS AND OUTCOME MEASURES	15
	Objectives	15
	Endpoints	16
	Outcome Measures	16
	ELIGIBILITY CRITERIA	17
	Inclusion Criteria	17
	Exclusion Criteria	18
	SUBJECT REGISTRATION	19
	TREATMENT PLAN	20
	Pre-medication	20
	Drug Administration	20
	Supportive Care:	20
	Concurrent Therapy	20
	Restrictions during the study	21
	DOSE MODIFICATIONS	22
	Dose Modifications	22
	STUDY CALENDAR & EVALUATIONS	
	Screening	
	On Treatment	
	Protocol therapy discontinuation	54
	Safety Follow-up: 30 days (±7 days) after last dose of protocol therapy	54
	At Recurrence:	55
	Follow-up	55
	CRITERIA FOR DISEASE EVALUATION	55
	BIOLOGICAL CORRELATIVES	57
	DRUG INFORMATION	59
	Drug Names:	
	Drug Class:	
	Formulation, Packaging and Storage	
	Availability and Distribution	
	Preparation	60
	Administration	
	Precautions	
	Side Effects	
	ADVERSE EVENTS	
	Definitions	61
	Reporting	65
	IND Safety Reports Unrelated to This Trial	68

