12.12. Analysis Plan for Primary Objectives/Aims

In the efficacy evaluable population, our primary analysis will be to estimate RPS at 1 year with a 95% confidence interval. Kaplan-Meier curve will also be estimated for the relapse free survival curve.

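### The no-go cutoff of 15 relapse-free patients was set for 23 evaluable patients; applied to the 34 now planned, it gives a type I error of about 70% instead of 5%

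*Combined protocol and SAP*

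**What the plan says.** Section 12.6 sets a null under which 1-year relapse-free survival (RFS) after "neoadjuvant chemoradiotherapy and esophagectomy is 50% or less" and an alternative under which it is "neoadjuvant chemoradiotherapy and esophagectomy is 75% or greater". It allows a "type I error (the probability of concluding that the drug is effective when it is actually not effective) of 0.05" and a type II error of 0.20, and arrives at 23 evaluable patients. The decision rule follows: "If the total number of patients free of relapse at 1 year is less than or equal to 15", the drug is not considered for further study. The Study Design entry of the synopsis repeats it: "If total number of patients free of disease relapse at 1 year is less than or equal to 15".

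Both places then enlarge the trial so that 1-year RFS is estimated more precisely. Section 12.6 gives a "target of 39 enrolled and at least 34 patients evaluable for 1 year RFS", and the synopsis gives the current size as "Total n=39, 34 efficacy evaluable and allowing for up to 5 unevaluable". The synopsis keeps the 50% and 75% hypotheses, the 5% alpha and the 80% power beside this larger number.

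Section 12.2 describes a single-stage design. Section 12.12 says that, in the efficacy evaluable population, "our primary analysis will be to estimate RPS at 1 year with a 95% confidence interval" (RPS is presumably a slip for RFS). It names no test and no threshold.

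**The concern.** A cutoff expressed as a count means something only together with its denominator. Fifteen was chosen for 23 patients; the sample grew by about half and the count stayed the same. The rule speaks of a total number of patients, and neither 12.6, 12.12 nor the definition of the efficacy evaluable population in 12.8 sets aside a subset of 23.

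The primary objective is to determine whether durvalumab improves 1-year RFS over the historical rate, and this cutoff is the only written rule that answers it. Applied to the planned analysis population, it would usually pass a drug that does no better than the 50% null. If it was meant only for the first 23, the plan does not say so, nor which 23. The denominator could then be chosen once the results are known. At 34 evaluable patients, the choice matters for any result from 16 to 22 relapse free: such a result clears the written cutoff but fails an exact 5% test.

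**Working it through.** **Inputs.** Null rate 0.50, alternative 0.75, type I error 0.05, type II error 0.20, 23 evaluable patients and no-go at 15 or fewer (12.6). Current size: at least 34 evaluable, 39 enrolled (12.6 and synopsis). Two readings are mine. First, no-go at 15 or fewer is taken to mean go at 16 or more. Second, the test is taken as one-sided, because the hypotheses are directional. Both are supported by the reproduction below.

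**Formula.** For a go rule of k or more relapse free out of n, P(go | p) = Σ from x = k to n of C(n, x) pˣ (1 − p)ⁿ⁻ˣ. The type I error is this probability at p = 0.50, and the power is its value at p = 0.75.

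**Step 1: the plan's own figures.** With n = 23 and k = 16, the type I error is 0.0466 and the power 0.804. This is the smallest n that meets both targets. The one-sided normal approximation agrees: [(1.645 × √0.25 + 0.842 × √0.1875) / 0.25]² = 22.5, rounded up to 23. A two-sided 5% test would need 28.9, rounded up to 29, so the design was one-sided. The original calculation is correct.

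**Step 2: the same cutoff at the current size.**

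| Evaluable n | 16/n | Type I error, go at 16 or more |
|---|---|---|
| 23 | 69.6% | 0.047 |
| 34 | 47.1% | 0.696 |
| 35 | 45.7% | 0.750 |
| 36 | 44.4% | 0.797 |
| 37 | 43.2% | 0.838 |
| 38 | 42.1% | 0.872 |
| 39 | 41.0% | 0.900 |

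At n = 34 the error is 0.696 / 0.05 ≈ 14 times the stated limit. Even if true 1-year RFS were 40%, below the null, P(go) would be 0.25. A result of 16/34 has an exact (Clopper-Pearson) 95% interval of 29.8% to 64.9%.

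**Step 3: cutoffs that respect 5%.** The smallest k with P(X ≥ k | n, 0.50) ≤ 0.05 is:

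| Evaluable n | Go if at least | Type I error | Power at 75% |
|---|---|---|---|
| 34 | 23 | 0.029 | 0.881 |
| 35 | 23 | 0.045 | 0.924 |
| 36 | 24 | 0.033 | 0.908 |
| 37 | 24 | 0.049 | 0.942 |
| 38 | 25 | 0.037 | 0.929 |
| 39 | 26 | 0.027 | 0.914 |

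At n = 34, going at 22 would give 0.061 and exceed the limit. Power is above 80% in every row.

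**The case against.** The best reply is that the rule belongs to the 23-patient design. In 12.6 and in the synopsis the cutoff appears with the 23-patient calculation, before the extra patients are introduced, and their stated purpose is precision alone. On that reading the type I error stays at 0.0466 and no figure in the plan is wrong. The reading is plausible, and it makes the 70% conditional on applying the rule to everyone. But it is not written anywhere: the rule counts a total, the design has a single stage and so no look at 23, and the synopsis sets the 5% and 80% beside the larger sample. It would also leave 11 of 34 evaluable patients out of the go decision, though they would still contribute to the estimate and the Kaplan-Meier curve.

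A second reply is that the primary analysis is now estimation, so 16/34 would be reported with an interval that plainly includes 50%. This limits the practical harm, but 12.12 does not make the interval a success criterion.

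It is also true that the text never says that 16 or more means go. That is an inference, but the stated error rates are met at n = 23 with exactly this rule.

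**Conclusion.** The concern holds. The only efficacy decision rule in the plan is not tied to the number of patients now to be analysed. Applied to the planned evaluable population, it has a type I error of 0.70 at 34 and up to 0.90 at 39, against a stated 0.05, and it accepts an observed rate below the null. These figures assume that 16 or more means go and that all evaluable patients are counted. Limiting the rule to the first 23 evaluable patients would restore 0.047, but that restriction has to be written. Either way the text must change before the primary analysis.

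**What to change.** In 12.6 and the synopsis, replace the cutoff of 15 with one for the number actually evaluable: go if at least 23/34, 23/35, 24/36, 24/37, 25/38 or 26/39 are relapse free at 1 year. State the exact one-sided type I error and the power for each (0.027 to 0.049 and 0.88 to 0.94).

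Add the same one-sided exact binomial test against 50% to 12.12, and say that the test, not the two-sided 95% interval, decides. The two can disagree: at 23/34 the one-sided p-value is 0.029, which is above 0.025, so an exact two-sided 95% interval would still just include 50%.

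If the rule is meant only for the first 23 evaluable patients, say so in both places, fix the order (for example by registration), state how replaced subjects are handled, and say that the remaining patients serve estimation only.

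The cost is protocol wording, with no extra patients. At 34 evaluable the bar rises from 16 to 23. As a proportion, 23/34 (67.6%) is slightly below the 16/23 (69.6%) of the 23-patient design.

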12.7. Criteria for Stopping the Study

Safety: The first six subjects treated with at least one dose of study drug will be observed for a minimum of 60 days. During the 6th subject's 60-day observation period, further accrual will be halted to evaluate "unacceptable toxicities warranting early closure of the trial" defined as:

- 1) Any definitive durvalumab-related death. A durvalumab-related death will be continuously monitored throughout the trial and the trial will be suspended for re-evaluation whenever such an event is confirmed.
- 2) Any unexpected and previously unreported grade 4 toxicities definitely related to durvalumab.

If such events are observed in one subject, the DSMB will discuss and provide recommendations to the sponsor-investigator. If such events are observed in two or more subjects, the trial will be suspended for re-evaluation.

Pneumonitis of grade 3 and 4 will be continuously monitored. An overall rate of 20% or above would be considered unacceptable. If the probability of the grade 3/4 pneumonitis rate being less than 20% drops below 0.1, the trial will be suspended for re-evaluation.

Population	Definition
Enrolled	This will comprise all patients who meet the eligibility criteria and are registered onto the study.
Efficacy Evaluable	This will comprise all patients who receive at least one dose of trial drug and either undergo at least one post-baseline assessment or die before any evaluation.
Safety	This will comprise all patients that receive at least one dose of durvalumab

12.8. Analysis Datasets

12.9. Subject Characteristics and significant protocol violations

Subject demographics and subject baseline clinical characteristics will be listed and summarized for all subjects enrolled, including age, gender, and race by phase. Counts, means, medians, standard deviation, minimum and maximum values will be presented. Significant protocol violations will be listed.

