1.2.4.1 Adverse Event Profile of Durvalumab (MEDI4736) Monotherapy

Study CD-ON-MEDI4736-1108: The safety profile of MEDI4736 monotherapy in the 694 subjects with advanced solid tumors treated at 10 mg/kg Q2W in Study CD-ON-MEDI4736-1108 has been broadly consistent with that of the overall 1,279 subjects who have received MEDI4736 monotherapy (not including subjects treated with blinded investigational product) across the clinical

development program. The majority of treatment-related AEs were manageable with dose delays, symptomatic treatment, and in the case of events suspected to have an immune basis, the use of established treatment guidelines for immune-mediated toxicity. As of 07May2015, among the 694 subjects treated with MEDI4736 10 mg/kg Q2W in Study CD-ON-MEDI4736-1108, a total of 378 subjects (54.5%) experienced a treatment-related AE, with the most frequent (occurring in \geq 5% of subjects) being fatigue (17.7%), nausea (8.6%), diarrhea (7.3%), decreased appetite (6.8%), pruritus (6.3%), rash (6.1%), and vomiting (5.0%). A majority of the treatment-related AEs were Grade 1 or Grade 2 in severity with \geq Grade 3 events occurring in 65 subjects (9.4%). Treatment-related \geq Grade 3 events reported in 3 or more subjects ($\geq 0.4\%$) were fatigue (12 subjects, 1.7%); increased aspartate aminotransferase (AST; 7 subjects, 1.0%); increased gamma-glutamyltransferase (GGT; 6 subjects, 0.9%); increased alanine aminotransferase (ALT; 5 subjects, 0.7%); and colitis, vomiting, decreased appetite, and hyponatremia (3 subjects, 0.4% each). Six subjects had treatmentrelated Grade 4 AEs (upper gastrointestinal hemorrhage, increased AST, dyspnea, neutropenia, colitis, diarrhea, and pneumonitis) and 1 subject had a treatment-related Grade 5 event (pneumonia). Treatment-related serious adverse events (SAEs) that occurred in ≥ 2 subjects were colitis and pneumonitis (3 subjects each). A majority of the treatment-related SAEs were \geq Grade 3 in severity and resolved with or without sequelae. AEs that resulted in permanent discontinuation of MEDI4736 were considered as treatment related in 18 subjects (2.6%), with colitis being the most frequent treatment-related AE resulting in discontinuation (3 subjects). A majority of the treatment-related AEs resulting in discontinuation of MEDI4736 were \geq Grade 3 in severity and resolved with or without sequelae.

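### The pneumonitis suspension rule counts only grades 3 and 4, so a pneumonitis recorded as grade 5 is not an event for it, and the death rule covers such a case reliably only when it is rated definite

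*Combined protocol and SAP*

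**What the plan says.** Section 12.7 (Criteria for Stopping the Study) has three safety criteria, repeated in the study design part of the synopsis.

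- **Pneumonitis rule.** "Pneumonitis of grade 3 and 4 will be continuously monitored". The limit is "An overall rate of 20% or above would be considered unacceptable". The action is "If the probability of the grade 3/4 pneumonitis rate being less than 20% drops below 0.1, the trial will be suspended for re-evaluation". There is no causality condition. Grade 5, worst-grade scoring, the denominator and the prior are not mentioned.
- **Death rule.** It is defined as "Any definitive durvalumab-related death". The next sentence reads "A durvalumab-related death will be continuously monitored throughout the trial and the trial will be suspended for re-evaluation whenever such an event is confirmed", without the word *definitive*.
- **Other toxicity rule.** "Any unexpected and previously unreported grade 4 toxicities definitely related to durvalumab".

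Section 6 grades adverse events by CTCAE version 4. Section 11.1.6 lists five causality ratings (unrelated, unlikely, possible, probable, definite) and treats an event as related when the drug could reasonably have caused it. Section 11.2.3.2 counts possible, probable and definite as reasonably related. *Definitive* is not one of the listed ratings.

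**The concern.** Pneumonitis is the one toxicity that the trial monitors against a rate with a probability threshold, and that rule stops at grade 4. A grade 3 pneumonitis rated unrelated counts, but a pneumonitis recorded as grade 5 and rated probable does not. No reason is given for leaving out the most severe grade.

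The other two criteria do not clearly fill the gap. The death rule is defined by the top causality rating. The remaining rule is limited to grade 4 events that are unexpected and previously unreported, whereas Section 10.8 lists pneumonitis as an identified risk. These patients have had concurrent chemoradiotherapy and esophagectomy, so a fatal lung event could plausibly be rated below definite. At stake is whether the rule reaches its trigger when some of the severe cases are fatal.

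**Working it through.** The plan prints no boundary and no operating characteristics for this rule, so there is no stated figure to reproduce. The check has three parts.

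**1. Where a pneumonitis recorded only as grade 5 falls, by causality rating**

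| Rating (11.1.6) | Pneumonitis rule | Death rule |
|---|---|---|
| Definite | not counted | covered |
| Possible or probable | not counted | ambiguous: outside the defining sentence, arguably inside the action sentence |
| Unlikely or unrelated | not counted | not covered on any reading |

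A grade 3 or 4 pneumonitis is counted by the pneumonitis rule in all three rows.

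**2. Effect of one uncounted case**

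Inputs from 12.7: limit 20%, trigger 0.1. Assumptions: a Beta(a, b) prior, worst-grade scoring, and the fatal case kept in the denominator as a non-event.

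Formula: P(rate < 20% given x of n) = the Beta(a + x, b + n − x) distribution function at 0.20. The rule suspends when this is below 0.1. For Beta(1,1) it equals P(Binomial(n + 1, 0.2) ≥ x + 1). For 4 of 12 that is P(Binomial(13, 0.2) ≥ 5) = 0.0991, and for 3 of 12 it is P(Binomial(13, 0.2) ≥ 4) = 0.2527.

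| n | Beta(1,1): boundary count, P | one case uncounted | Beta(0.4,1.6): boundary count, P | one case uncounted |
|---|---|---|---|---|
| 6 | 3, 0.0333 | 0.1480 | 3, 0.0861 | 0.2928 |
| 12 | 4, 0.0991 | 0.2527 | 5, 0.0634 | 0.1792 |
| 20 | 7, 0.0431 | 0.1085 | 7, 0.0765 | 0.1741 |
| 34 | 10, 0.0747 | 0.1457 | 11, 0.0555 | 0.1130 |

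Every row goes from suspend to continue. That is true by construction, because the boundary is the smallest count that suspends. The prior decides which count is the boundary: under Beta(0.4,1.6), 4 of 12 gives 0.179 and 10 of 34 gives 0.113, so neither suspends even with every case counted.

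If the fatal patient is instead removed from both counts, the observed rate still falls (3/6 = 50% becomes 2/5 = 40%), but the action does not always change. Under Beta(1,1), 2/5 gives 0.0989 and 6/19 gives 0.0867 (both still suspend), while 3/9 gives 0.1209 and 10/38 gives 0.1406 (both continue).

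**3. Effect over the whole trial**

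Assumptions: a look after every patient up to 39, a true grade 3–5 rate p, and a share f of cases that are fatal and uncounted, so the counted rate is p(1 − f). With p = 30% and f = 25% the counted rate is 0.30 × 0.75 = 22.5%.

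| p | f | Prior | P(ever suspend), grades 3–5 | P(ever suspend), grades 3–4 |
|---|---|---|---|---|
| 30% | 25% | Beta(1,1) | 0.86 | 0.60 |
| 30% | 25% | Beta(0.4,1.6) | 0.74 | 0.40 |
| 20% | 10% | Beta(1,1) | 0.50 | 0.42 |
| 10% | 10% | Beta(1,1) | 0.16 | 0.14 |
| 5% | 10% | Beta(1,1) | 0.07 | 0.06 |

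The documents give neither p nor f for this population, so these rows show a range and are not forecasts.

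**The case against.** A reader might infer that any fatal pneumonitis not rated definite is counted nowhere. The documents do not support that as a fact. The second sentence of the death rule drops *definitive*. Read with the definition of related in 11.1.6, a single possible or probable fatal case could suspend the trial outright, which is stronger than any pneumonitis count. The phrase about such an event more naturally points back to the definitive death, but both readings are open. Only the unlikely and unrelated ratings escape on every reading.

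A reader might also infer that a fatal case always lowers the monitored rate. That depends on scoring and denominator conventions that 12.7 does not state. Section 11.2.2.1 reports progression of a serious event as follow-up to the original, so a case first recorded at grade 3 or 4 may already be in the numerator when the patient dies.

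Third, "1 subject had a treatment-related Grade 5 event (pneumonia" in Section 1.2.4.1 might be taken as evidence of fatal pneumonitis on this drug. The event is pneumonia, so it shows only that the protocol uses grade 5 as a category. In ATLANTIC (1.2.4.1), 3 of 303 patients had treatment-related grade 3 pneumonitis and there were no treatment-related grade 4 or 5 events. That is a different population, but at low rates the gap has little effect, as the last two rows of the final table show.

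Finally, a fatal case would not go unseen. Pneumonitis must be reported within 24 hours whatever its attribution (11.1.3, 11.1.4), serious events within one business day (11.2.2.1), and an excess of grade 3 or higher events goes to the DSMC chair (13.1). The DSMB and DSMC can suspend the trial (13.1.1). All of that stands. None of these routes sets a numerical pneumonitis threshold for suspension, which is what the rule in 12.7 is for.

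**Conclusion.** The concern holds in a limited form. On its plain wording the pneumonitis rule leaves out a case recorded as grade 5. The death rule makes up for this with certainty only for a definite rating, leaves possible and probable ratings ambiguous, and does not reach unlikely or unrelated ones.

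Under worst-grade scoring with the patient kept in the denominator, one such case at the boundary is enough to prevent suspension under the priors tabulated. Across the trial the loss ranges from about 0.01 in the chance of suspension (true rate 5%, one case in ten fatal) to about 0.34 (true rate 30%, one in four fatal, Beta(0.4,1.6)). These sizes rest on assumed priors, rates and fatal shares. The finding about the wording does not.

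**What to change.** - In 12.7 and the synopsis, define the monitored event as pneumonitis of grade 3 or higher (grades 3–5), scored by worst grade, among all patients who received at least one dose. Use the same definition in the trigger sentence, and leave the 20% and 0.1 figures as they are.
- Reconcile the two sentences of the death rule so that they name the same causality ratings, using the category labels in 11.1.6. Which ratings apply is for the sponsor-investigator and the DSMB to decide.

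**Cost.** A few words in two places, with no change to sample size, endpoint or data collection. The downside is a slightly higher chance of a pause for re-evaluation, for example 0.16 against 0.14 at a true 10% rate with one case in ten fatal under Beta(1,1).

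The unstated prior and the missing table of integer boundaries are a separate, secondary point. They could be settled in the same edit, since at a true 20% rate with every case counted the chance of suspension runs from 0.50 under Beta(1,1) to 0.18 under Beta(2,8).
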